3 DEFINITIONS OF TERMS

Term	Definition
Acute sinusitis (AS)	Per the 2016 “International Consensus Statement on Allergy and Rhinology” definition, patient must have inflammation lasting < 4 weeks associated with the sudden onset of symptoms such as nasal blockage/obstruction/congestion or nasal discharge (anterior/posterior) and facial pain/pressure or reduction/loss of smell.
Adverse event (AE)	Any untoward medical occurrence associated with the use of a drug in humans, whether or not considered drug related. [21 CFR 312; BN ES ISO14155]
Adhesion grading scale	Adhesion severity graded on a 5-point scale from 0 to 4 at the screening and baseline visits, as follows: 0: None 1: Small but non-obstructing (no separation required) 2: Obstructing, but easily separated 3: Dense and obstructing, separation difficult 4: Severe: complete adhesion of the middle turbinate to the lateral nasal wall
Bilateral polyp grade	Sum of left and right polyp grades (see - scale below), resulting in a bilateral polyp grade of 0 to 8
Case report form (CRF)	Standardized forms designed to capture monitored data as required by the protocol.
Chronic rhinosinusitis with nasal polyps	Per the 2016 “International Consensus Statement on Allergy and Rhinology” definition, patient must have ≥ 12 weeks of: 
 • Two or more of the following symptoms: 
 ○ Mucopurulent discharge (rhinorrhea or postnasal drip) ○ Nasal obstruction and congestion ○ Decreased/absent sense of smell ○ Facial pressure/pain • And one or more of the following findings: 
 ○ Evidence of inflammation on paranasal sinus examination or computed tomography ○ Evidence of purulence coming from paranasal sinuses or ostiomeatal complex • And presence of polyps.
Enrolled	Subjects are considered enrolled upon signing the informed consent form.
High-dose steroids	The following steroids are considered as high-dose in the study: oral, parenteral, injections, budesonide or other sinus steroid irrigations, rinses or drops, nebulized steroids administered nasally.

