12 CONCOMITANT MEDICATION

The study standardized medication regimen will be as follows:

- Leading up to the baseline procedure, there is a 30-day restriction for use of parenteral and injected steroids (e.g., Kenalog injection), and monoclonal antibodies (e.g., Dupixent, Nucala, Xolair) 1
- Leading up to the baseline procedure, a 14-day restriction for use of oral steroids, budesonide or other sinus steroid irrigations/rinses, nebulized steroids administered nasally or budesonide drops.
- After the baseline procedure, subjects will be encouraged to use saline rinses regularly through Day 365.
- After the baseline procedure, subjects will be required to use MFNS 200 mcg (two sprays in each nostril) once daily throughout the entire duration of the follow-up, unless the use of MFNS is not warranted clinically. Both the generic version of MFNS by Apotex or Novartis and the brand-name version by Merck (Nasonex) can be used.
- High-dose steroids (e.g., oral, parenteral, injections, budesonide or other sinus steroid irrigations, rinses or drops, nebulized steroids administered nasally) will be allowed during the study follow-up only if clinically necessary (see Section 13 *Medical and Surgical Interventions*).
- Orally-inhaled steroids for control of asthma will be permitted.
- If infection is suspected at any time during the study, treatment with antibiotics will be permitted.

- Use of monoclonal antibodies is prohibited during the 365-day follow-up period.
- To the extent possible, subjects will be maintained on stable regimens of leukotriene inhibitors and/or immunotherapy (e.g., Montelukast, Zafirleukast, Zileuton) for allergies through Day 365, if currently on such regimens; however, use of breath-powered or other methods of intranasal steroid delivery for allergies is not permitted during the study.
- Use of drug-eluting implants (PROPEL[®], PROPEL[®] Mini, PROPEL[®] Contour) is prohibited during the baseline procedure and throughout the 365-day follow-up period, unless placed immediately following RESS performed in the operating room setting.

All sinus-related and AE-related medications will be recorded in EDC, including their full brand/trade or generic names (whichever prescribed), dose, frequency, indication, start and end dates. Each AE will be coded using the Medical Dictionary for Regulatory Activities (MedDRA) and presented based on the system organ class (SOC) and preferred term.

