4.3 Other Endpoints

Implant delivery success rate

Percentage of successful deployments of the S8 Sinus Implant to the target site per total number of sinuses attempted during the baseline and repeat placement procedures.

Interventions received

Proportion of subjects who received interventions (i.e., steroids or antibiotics for ethmoid sinus obstruction or for other reasons, polypectomy, repeat endoscopic sinus surgery) through Day 365.

Responder rates: Proportion of subjects who were responders as defined by nasal obstruction/congestion and bilateral polyp grade.

Indicated for repeat endoscopic sinus surgery (RESS) based on clinical data: Proportion of subjects who are indicated for RESS based on nasal obstruction/congestion score ≥ 2 and polyp grade ≥ 2 on each side.

Implant status: Proportion of sinuses with implant status of present, absent, or removed.

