7.3 Medical or Surgical Interventions

Since high-dose steroids (e.g., oral, parenteral, injection, budesonide or other sinus steroid irrigations, rinses or drops, nebulized steroids administered nasally) or surgical intervention may confound the efficacy measures, the following method will be applied to the analyses in cases where such interventions are performed:

- If a subject initiates high-dose steroids (see Clinical Study Protocol Appendix A for a list of medications considered as high-dose steroids) or undergoes polypectomy or revision ESS for chronic sinusitis conditions attributable to the ethmoid sinus during the study, this represents treatment failure.
- For subjects with interventions for treatment failure occurring at any time point through Day 180 (regardless of receiving repeat implant placement at Day 90), the last available scores for Nasal Obstruction/Congestion, SNOT-22, and endoscopic measures prior to interventions will be carried forward to all time points through Day 180 or the last follow-up visit.

No other data imputation rules will be applied in the planned statistical analyses. All efficacy endpoints will be presented as intervention-adjusted values.

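### SAP 7.3's closed list of confounding interventions omits monoclonal antibodies, so scores after a prohibited start for nasal polyps would enter the intervention-adjusted efficacy summaries as observed

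*SAP*

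**What the plan says.** SAP 7.3 starts from the premise that some treatments given during follow-up confound the efficacy measures. It names two triggers. The first is drug treatment: "If a subject initiates high-dose steroids (see Clinical Study Protocol Appendix A for a list of medications considered as high-dose steroids"). The second is surgery: a subject who "undergoes polypectomy or revision ESS for chronic sinusitis conditions attributable to the ethmoid sinus during the study, this represents treatment failure". After either one, the last scores before the intervention are carried forward through Day 180 or the last visit. The section ends with "No other data imputation rules will be applied in the planned statistical analyses" and "All efficacy endpoints will be presented as intervention-adjusted values".

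The drug trigger covers steroids only. Protocol section 3 defines it so: "The following steroids are considered as high-dose in the study: oral, parenteral, injections, budesonide or other sinus steroid irrigations, rinses or drops", plus nasally nebulised steroids. Appendix A of the protocol lists steroids. The carry-forward from unscheduled visits in SAP 6.4 is also tied to high-dose steroids.

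Protocol 10.2 excludes patients who used a monoclonal antibody for asthma, allergies or nasal polyps in the 30 days before baseline, and patients who need one during the study. Protocol 12 adds: "Use of monoclonal antibodies is prohibited during the 365-day follow-up period". Neither document says how scores recorded after such use are analysed.

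**The concern.** A subject who starts budesonide rinses for polyps is held at the pre-rinse scores. A subject who starts an antibody for polyps and stays in follow-up is analysed on the scores reached with the antibody. Both have received another treatment for the disease under study, so the second case falls under SAP 7.3's own reason for adjusting, yet the rule leaves it out.

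Because the list is closed and only adjusted values are planned, this is a written rule that gives a favourable bias in that case, not a detail left open. At stake are the mean changes from baseline and the responder rates at visits after the start, through Day 180, and the Day 180 proportion indicated for repeat surgery. The study has one arm and one analysis population, so neither a control group nor a per-protocol set would reveal the effect.

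**Working it through.** The plan gives no figure for this point. Its one computed figure, 100 + 85 = 185 implant procedures (Protocol 16.1, SAP 7.2), adds up but has no bearing here. The check is first logical, then arithmetic.

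**Step 1: can the text reach an antibody?**
- Steroid trigger: no, because an antibody is not a steroid. The Appendix A note that the list is incomplete and that doubtful cases are reviewed individually extends a list of steroids; it does not change the class.
- Surgical trigger: no.
- Any other rule: no, because SAP 7.3 excludes further imputation.
- Removal from the analysis: not assured. Protocol 10.3 permits withdrawal for non-compliance but does not require it. Protocol 17.2.2 makes prohibited use a deviation without an analysis consequence. SAP 5.0 uses the safety population throughout.

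So a subject who starts an antibody and stays in follow-up contributes observed scores.

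**Step 2: how large could the effect be?**
Input from the documents: n = 50 treated subjects. Assumed, because the documents do not give them: k, the number who have started an antibody and responded by the visit in question, and d, the improvement per subject after the start relative to the last score before it.
- Largest shift in a responder rate: k/n. For one subject, 1/50 = 2 percentage points.
- Shift in a mean change: k × d/n. For one subject with d = 3 grades, 3/50 = 0.06 grade.

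| k (assumed) | Responder rate, at most | Mean bilateral polyp grade, d = 1 to 4 | Mean obstruction/congestion score, d = 0.5 to 2 |
|---|---|---|---|
| 0 | 0 | 0 | 0 |
| 1 | 2 points | 0.02 to 0.08 | 0.01 to 0.04 |
| 3 | 6 points | 0.06 to 0.24 | 0.03 to 0.12 |
| 5 | 10 points | 0.10 to 0.40 | 0.05 to 0.20 |

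These figures take all 50 subjects as observed at the visit. With fewer, replace 50 by the number observed.

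**Step 3: an illustration.** Suppose 30 of 50 subjects are responders and three of them owe it to an antibody. The reported rate is 30/50 = 60% (exact 95% CI 45.2 to 73.6). With carry-forward it is 27/50 = 54% (39.3 to 68.2).

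**The case against.** The strongest reply is that the protocol is built to prevent this event. Antibodies are excluded at entry and banned for the year, and a subject withdrawn on switching contributes no later scores. SAP 7.3 deals with the rescue treatments that Protocol 13 allows, which are the foreseeable ones. The sole objective is safety, efficacy is summarised descriptively without a success threshold, and in the illustration the shift lies well inside the confidence interval. All of this limits the size and likelihood of the effect. It does not supply a rule: a ban says nothing about analysis, withdrawal is optional, and a withdrawn subject would still not count as a failure.

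Four stronger readings are tempting, and the documents do not support them.
- *That a switch would go unreported.* SAP 4.3 does list only "steroids or antibiotics for ethmoid sinus obstruction or for other reasons, polypectomy, repeat endoscopic sinus surgery". But Protocol 4, Protocol 9.3 and SAP 7.4 define the same endpoint to include sinus-related medications, which an antibody for polyps fits, and SAP 7.5 tabulates all concomitant medications. What remains is a mismatch of wording between SAP 4.3 and the other three places. Counting the drug still does not adjust the scores.
- *That prohibited intranasal steroid devices fall through the same gap.* Protocol 12 says that "use of breath-powered or other methods of intranasal steroid delivery for allergies is not permitted during the study". That ban concerns allergies, and the drug is a steroid, so the individual review in Appendix A can reach it.
- *That any antibody start shows that the implant failed.* SAP 7.3 ties failure to sinusitis attributable to the ethmoid sinus. A start for asthma or allergy may confound the scores but is not failure in that sense.
- *That the efficacy results are inflated.* The documents give no count of switchers, so this cannot be said.

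**Conclusion.** The gap is real but conditional. As written, SAP 7.3 would analyse a subject who starts an antibody for nasal polyps or sinusitis before Day 180, and who remains in follow-up, on the scores reached with that drug, contrary to the section's own rationale.

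The size rests on two assumptions, the number of switchers and their improvement after the start. Each switcher moves a responder rate by at most 2 points and the mean bilateral grade by d/50, with all 50 subjects observed. A subject who had already improved before the start adds less to the mean and may add nothing to a responder row. Only visits after the start are affected, so a full multi-subject shift at Day 120 would need every one of them to have started and responded by then. Starts after Day 180 do not touch the efficacy endpoints.

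**What to change.** Before database lock:
1. In the first bullet of SAP 7.3, add to the events that count as treatment failure and trigger carry-forward of the last pre-start scores: *or starts a monoclonal antibody for nasal polyps or chronic sinusitis*.
2. For an antibody started for asthma or allergy, do not label the subject a failure. Show a sensitivity summary in which scores after the start are replaced by the last value before it.
3. Align the SAP 4.3 list of interventions with the sinus-related medications wording of SAP 7.4 and Protocol 9.3, so that an antibody for polyps is counted wherever the endpoint is defined.

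The cost is one clause, one added term in the medication flag, one conditional sensitivity summary and a wording change. Protocol 12 already requires indication and start date for sinus-related and AE-related medications. That does not clearly cover every antibody for asthma or allergy, so check that those start dates are available. If anyone switches, the descriptive efficacy summaries become slightly less favourable; the safety analyses do not change. Deciding now also keeps the handling a priori under SAP 6.5; after lock it would be post hoc.

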7.4 Efficacy and Other Endpoints

Continuous measures are analyzed using descriptive statistics such as means, medians, and SD. and, where appropriate, 95% CI for the mean assuming a normal distribution.

Continuous measures include:

- Nasal Obstruction/Congestion score: Change from baseline to each time-point (Days 30, 60, 90, 120, 150, 180) in the mean score (scale 0 to 3)
- SNOT-22 score: Change from baseline to each time-point (Days 30, 60, 90, 120, 150, 180) in SNOT-22 total score, domain scores, and individual symptom scores. The total score of SNOT-22 is calculated as the sum of all items, and ranges from 0 to 110 with the highest score representing worsening. The following table lists corresponding items and ranges for each symptom domain.

SNOT-22 Domains	Survey Items	Score Range
Rhinologic Symptoms	#1, #2, #3, #6, #21, #22	0–30
Extra-Nasal Rhinologic Symptoms	#4, #5, #6	0–15
Ear/Facial Symptoms	#2, #7, #8, #9, #10	0–25
Psychological Dysfunction	#14, #15, #16, #17, #18, #19, #20	0–35
Sleep Dysfunction	#11, #12, #13, #14, #15	0–25

- Bilateral Polyp Grade: Change from baseline to each time-point (Days 30, 60, 90, 120, 150, 180) in bilateral polyp grade (scale 0 to 8), which represents a sum of left and right sides. The bilateral polyp grade for a given patient is set as missing if the grade for one side is missing.
- Percent Ethmoid Sinus Obstruction: Change from baseline to each time-point (Days 30, 60, 90, 120, 150, 180) in percent ethmoid sinus obstruction (scale 0% to 100%). Percent ethmoid obstruction scores on left and right sides are averaged for each subject at each time point. The results for a given patient is set as missing if the score for one side is missing.

Categorical measures are analyzed as counts, rates, proportions and frequencies. Where it is appropriate, 95% CI (computed using the exact method) and p-values will be presented.

Categorical measures include:

- Implant delivery success rate: Proportion of successful deployments of the S8 Sinus Implant to the target site per total number of sinuses attempted including the baseline and repeat placement procedures. Implant delivery success rate at Baseline, Day 90 and Baseline & Day 90 combined will be presented.

- Interventions received: Proportion of subjects who received interventions (i.e., sinus-related medications, systemic steroid interventions, and surgical interventions) through Day 365.
- Responder rates: Proportion of subjects with clinically meaningful improvement from baseline in nasal obstruction/congestion score and/or bilateral polyp grade at each time-point (Days 30, 60, 90, 120, 150, 180) will be presented. Responders include subjects with:
 - Nasal obstruction/congestion score, ≥ 1.0 -point reduction from baseline
 - Nasal obstruction/congestion score, ≥ 2.0 -point reduction from baseline
 - Nasal obstruction/congestion score < 2.0
 - Bilateral polyp grade, ≥ 1.0 -point reduction from baseline
 - Bilateral polyp grade, ≥ 2.0 -point reduction from baseline
 - Polyp grade < 2 on each side
 - Nasal obstruction/congestion score ≥ 0.5 and bilateral polyp grade, ≥ 1.0 -point reduction
 - Nasal obstruction/congestion score ≥ 0.5 and bilateral polyp grade, ≥ 2.0 -point reduction
 - Nasal obstruction/congestion score ≥ 1.0 and bilateral polyp grade, ≥ 1.0 -point reduction
 - Nasal obstruction/congestion score ≥ 1.0 and bilateral polyp grade, ≥ 2.0 -point reduction
- Indicated for repeat endoscopic sinus surgery (RESS) based on clinical data: Proportion of subjects who are indicated for RESS based on nasal obstruction/congestion score ≥ 2 and polyp grade ≥ 2 on each side at Day 90 and at Day 180.
- Implant status: Proportion of subjects with implant status of present, absent, or removed, as assessed at each time-point (Days 30, 60, 90, 120, 150, 180).

7.5 Safety Evaluation

Adverse events

All adverse events (AE) will be coded using the Medical Dictionary for Regulatory Activities (MedDRA). Where possible, and if applicable, AE will be localized to a sinus type and side.

The incidence and percentages of AE and serious adverse events (SAE) through Day 365, including treatment emergent AE (TEAE), implant-related AE and SAE, will be presented by MedDRA system organ class (SOC) and preferred term (PT). Complete patient listings of all adverse events will be provided. For each adverse event, the following will be specified:

- Start and stop dates, and event onset (study day)
- The affected side (right or left) if available
- Seriousness
- Severity
- Strength of relationship if available
- Action taken
- Outcome

In tables presenting implant-related AE, the incidences and percentages will also be presented based on two mutually exclusive periods of observation:

- from baseline to Day 90 (before repeat placement)
- from repeat placement (at Day 90) to Day 180

Concomitant medications

Prior and concomitant medications are coded to therapeutic class and PT using the World Health Organization (WHO) Drug Dictionary. All concomitant medications are listed and summarized in a table.

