2.0 STUDY OBJECTIVE

To assess the safety of repeat placement of the S8 Sinus Implant when used in chronic sinusitis (CS) patients with recurrent nasal polyps.

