3.0 STUDY DESIGN

This is a prospective, non-randomized, open-label, multicenter clinical trial enrolling up to 50 subjects at up to 10 study centers across the U.S. Eligible subjects undergo in-office bilateral placement of the S8 Sinus Implant in the ethmoid sinuses (total of two implants). Subjects return for seven follow-up visits at Days 30, 60, 90, 120, 150, 180 and 365 (see Appendix A Schedule of Assessments). All implants are removed by Day 90. Subjects meeting eligibility criteria for repeat placement undergo repeat in-office placement of the S8 Sinus Implant in each ethmoid sinus with a nasal polyp grade ≥ 1 . All repeat implants are removed by Day 180.

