7.2 Sample Size

The 50-patient sample size was selected based on clinical judgment. In the RESOLVE II study, ~90% of sinuses had polyp grades ≥ 1 at Day 90. From this data, it is expected that of the 100 sinuses undergoing implant placement at baseline, greater than 85 sinuses would undergo repeat placements at Day 90. Therefore, a sample of 50 subjects will provide safety data on up to 185 implant procedures (100 implants at baseline; 85 implants at Day 90), which is deemed to be a large enough sample to detect potential additional implant-related adverse events associated with recurrent use of the implant.

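### Safety of repeat placement is the sole objective, but the plan reports only adverse-event counts and percentages, so the planned output does not show what risk is excluded.

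*SAP*

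**What the plan says.** SAP 2.0 and Protocol 8 give one objective: "To assess the safety of repeat placement of the S8 Sinus Implant when used in chronic sinusitis (CS) patients with recurrent nasal polyps". The trial has a single arm and no concurrent control (SAP 3.0).

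The adverse-event analysis is in SAP 7.5. It presents "The incidence and percentages of AE and serious adverse events (SAE) through Day 365, including treatment emergent AE (TEAE), implant-related AE and SAE" by system organ class and preferred term, with full listings. For implant-related events only, the counts and percentages are also split into baseline to Day 90 and repeat placement to Day 180. Protocol 16.2 says only that incidences will be presented. Neither section mentions an interval or a between-period difference.

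Intervals appear elsewhere. SAP 7.4 allows a 95% interval for means and, for its list of categorical efficacy and other measures, says: "Where it is appropriate, 95% CI (computed using the exact method) and p-values will be presented". Adverse events are not on that list. SAP 6.6 fixes the level of any interval that is presented but assigns none to adverse events.

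On sample size, SAP 7.2 states: "The 50-patient sample size was selected based on clinical judgment". It then calls the sample "deemed to be a large enough sample to detect potential additional implant-related adverse events associated with recurrent use of the implant". No event rate, probability or margin goes with that claim. SAP 5.0 defines one analysis population, everyone implanted at baseline. No subset is defined for those implanted again at Day 90.

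**The concern.** The sample-size text speaks of detecting additional events from recurrent use. That is a claim about what the data can reveal, and the two-period table is the natural place to examine it. Yet the table will hold two bare percentages from the same subjects. With few events, a low or equal percentage in the repeat period is easily read as reassurance, and nothing in the output shows how much risk remains compatible with it.

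The pairing is also lost. Two marginal percentages do not show how many subjects had an event only after the first placement or only after the repeat, so a reader of the tables cannot form a paired interval.

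Timing matters because SAP 6.5 classes any analysis designed after database lock as post hoc and exploratory. The bound on risk for the only objective would then have that status.

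**Working it through.** **The plan's own figure.** 50 subjects × 2 sinuses = 100 baseline implants. SAP 7.2 expects that "greater than 85 sinuses would undergo repeat placements at Day 90", and 100 + 85 = 185 procedures, as stated. The quoted rate of about 90% would give 90 repeats and 190 in total, so 85 is a rounded-down floor. There is no power or margin to reproduce.

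**Subjects informing the objective.** Only repeat placements bear on repeat use. At most two sinuses per subject gives 85 / 2 = 42.5, so at least 43 subjects; the maximum is 50. The range 43 to 50 is derived, and 45 is used below as an assumed middle value.

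**Zero events of a given type.** The exact two-sided 95% upper limit is 1 − 0.025^(1/n).

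| Unit | n | Upper limit |
|---|---|---|
| Re-implanted subjects | 43 | 8.2% |
| Re-implanted subjects (assumed) | 45 | 7.9% |
| Re-implanted subjects | 50 | 7.1% |
| Repeat sinuses, if sides were independent | 85 | 4.2% |

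If the two sides of a subject were fully correlated, the 85 sinuses would carry the information of the subjects alone, and 4.2% would move back to about 7.9% (45 subjects assumed).

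**Chance of seeing any event.** This is 1 − (1 − p)^n. At an assumed true rate of 2% per subject it is 58% for n = 43, 60% for n = 45 and 64% for n = 50.

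**Paired difference, repeat minus first period.** Let b be subjects affected only after the repeat and c those affected only after the first placement. The Wald interval is (b − c)/n ± 1.96 × √(b + c − (b − c)²/n)/n. Newcombe's paired interval combines the Wilson limits of the two percentages and allows for their correlation. All counts are assumed; n = 45 and no subject is affected in both periods.

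| b, c | Difference (points) | Wald 95% | Newcombe 95% |
|---|---|---|---|
| 0, 0 | 0 | 0 to 0 | −7.9 to +7.9 |
| 2, 2 | 0 | −8.7 to +8.7 | −11.0 to +11.0 |
| 5, 2 | +6.7 | −4.7 to +18.0 | −5.9 to +19.7 |

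In the first row both Wilson upper limits are 1.96²/(45 + 1.96²) = 3.84/48.84 = 7.9%, which gives the Newcombe limit. Wald collapses to zero width there, exactly where a bound is most needed. For 2 and 2, Newcombe's upper limit runs from 11.5 points (n = 43) to 10.0 (n = 50).

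**Denominator.** If 5 re-implanted subjects had an event in the repeat period, that is 5/50 = 10.0% of the SAP 5.0 population but 5/43 = 11.6% of re-implanted subjects in the smallest case.

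**The case against.** Descriptive adverse-event tables are normal in an open-label, single-arm study, and this plan states no hypothesis, margin or comparator. The objective can be read as describing safety during repeat use, not as comparing two periods. That stands, and it is why estimation is asked for here and not a test.

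A reader might infer more than the documents support, in four ways.

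- *That the study cannot say what risk it has excluded.* It can. Counts, percentages and listings with onset day are planned, so limits and the pairing could be worked out later. What is missing is a pre-specified display.
- *That all adverse events are split by period.* Only implant-related events are. Adverse events overall, treatment-emergent events and serious events are reported through Day 365. Splitting those too would need new tables.
- *That the SAP guarantees intervals for the lesser endpoints.* SAP 7.4 commits only to intervals where appropriate. The Appendix B mock-ups are not available here, so an interval column in the safety tables cannot be excluded. If one exists, a sentence in SAP 7.5 would reconcile text and tables.
- *That the between-period difference is the added risk of repeat placement.* It is not a clean measure of that. Baseline placement is always bilateral and other procedures are barred at that visit (Protocol 11.2). The Day 90 placement may be unilateral and may follow polypectomy, and only sinuses still at grade 1 or above are re-implanted (Protocol 11.3).

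**Conclusion.** The point holds as a gap in the planned output. The sole objective has no pre-specified measure of precision and no estimate of the contrast that the sample-size text invokes. On the plan's own expectation of repeat placements, zero events of a given type would still leave a subject-level rate of up to 8.2% to 7.1%. Zero in both periods would leave a paired increase of about 7.9 points, and two against two about 11 points (both for 45 subjects).

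The zero-event limits rest on 43 to 50 re-implanted subjects, derived from 85 sinuses. The paired figures rest on illustrative counts that no document gives. The difference is descriptive and should not be presented as a causal effect of the second implant.

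**What to change.** Amend SAP 7.5 before database lock.

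1. Add exact two-sided 95% intervals to the subject-level percentages for implant-related events in each of the two existing periods, and for serious events through Day 365.
2. For the repeat period, use subjects actually re-implanted at Day 90 as the denominator, and define that subset beside SAP 5.0.
3. For re-implanted subjects, report the paired difference in implant-related events (repeat minus first period) with a score-type paired 95% interval such as Newcombe's, not Wald. No test is needed.
4. Label the difference descriptive and name the reasons: bilateral against unilateral or bilateral exposure, and polypectomy barred at baseline but possible at Day 90.
5. State the upper limits in the study report next to the percentages.

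No new data are required. The cost is SAP wording, one subset definition and a few table columns. The real downside is that the intervals will be wide, so the safety statement will read less favourably than bare percentages would.
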